## Clinical Trials Unit

## **Revision History**

Version	Date	Author(s) and Role	Summary of Changes/Comments
0.1	23-12-2018	Trial statistician	Information from protocol included
0.2	14-02-2019	Trial statistician	Completing SAP
0.3	26-02-2019	Tṛial statistician	Changes made for collaborators' and senior statistician's comments on draft
0.4	14-03-2019	Trial statistician	Changes made for primary and secondary outcome measures

Date: 20/03/2019

#### LIST OF ABBREVIATIONS

AE Adverse event
AR Adverse reaction
BMI Body Mass Index
BP Blood pressure

CHD Coronary heart disease

CV Cardiovascular

CVD Cardiovascular disease EQ-5D EuroQoi five dimensions

HADS Hospital Anxiety and Depression Scale

ILS Immediate Life Support

ISWT Incremental Shuttle Walk Test

MI Myocardial Infarction

MVPA Moderate to Vigorous Physical Activity

PA Physical Activity

RCT Randomised Controlled Trial
REC Research Ethics Committee

RPAQ Recent Physical Activity Questionnaire

SAE Serious Adverse Event
SAR Serious Adverse Reaction
SOP Standard Operating Procedure

SUSAR Suspected Unexpected Serious Adverse Reactions

UHL University Hospitals of Leicester

v 1.0

20/03/2019

### 1 introduction

This Statistical Analysis Plan (SAP) outlines the proposed statistical analyses for the PACES study, where a detailed and comprehensive description of the statistical methods is provided. The PACES Study is a randomised controlled trial that is being conducted to assess the effectiveness of a low-cost pragmatic intervention to increase daily physical activity in participants 12-36 months post diagnosis of a cardiac event in order to reduce subsequent cardiovascular events.

The structure and content of this SAP provides sufficient detail to meet the requirements identified by the International Conference on Harmonization of Technical Requirements for Registration of Pharmaceuticals for Human Use (ICH): Guidance on Statistical Principles in Clinical Trials . All work planned and reported for this SAP will follow nationally and internationally accepted guidelines, published by the American Statistical Association and the Royal Statistical Society for statistical practice .

The purpose of this SAP is to outline the planned analyses that are to be performed on the data to support the completion of the study publication for protocol V6 13\_03\_18. The SAP will be amended if substantial changes are made to the planned analyses, and in any case, will be finalized before the database lock for this study. Exploratory post-hoc or unplanned analyses not necessarily identified in this SAP may be performed on these data as required. These analyses will be clearly identified in the study publication.

The reader of this SAP is encouraged also to read the clinical protocol for details on the conduct of this study, and the operational aspects of clinical assessments and timing for the process of completing a patient in this study.

The outlined boxes in this SAP represent information from the protocol. The analyses will be carried out by the Trial Statistician ([name]) and supervised by the Senior Statistician ([name]) to ensure the integrity of the data processing at all stages.

State of the State

Date:

20/03/2019

Clinical Trials Unit

### 1.1 Study Objectives

### 1.1.1 Primary objective

To assess the effectiveness of a low-cost pragmatic intervention to increase daily physical activity in participants at least 12-36 months post diagnosis of a cardiac event in order to reduce subsequent cardiovascular events.

### 1.1.2 Secondary objectives

- 1- To assess the effectiveness of a structured education intervention to improve CV risk factors such as smoking status, blood pressure, lipid profile, obesity, self-reported physical activity and objectively measured physical activity intensity.
- 2- To assess the acceptability, uptake and feasibility of implementing the programme in a population at high future risk of another CVD event in primary care.

### 1.2 Study design

## 1.2.1 Summary

The PACES study has been designed to facilitate service development; three main phases have been undertaken:

- 1. Development of the intervention for patients after a cardiac event.
- 2. Recruitment and training of the facilitators for programme delivery.
- 3. Delivery of a single centre, 2-arm parallel 12 month RCT to determine whether an education programme with text message support has an impact on the primary (average daily physical activity) and secondary outcomes (see section 2.2) compared with usual care.

Date:

20/03/2019

#### Clinical Trials Unit

#### 1.2.2 Randomisation

Participants will be randomised 1:1; stratified by gender (male; female) and ethnicity (White European; other) to either intervention or control groups.

If two people are taking part from the same household they will be randomised to the same arm to prevent contamination taking place.

Control participants will be sent a standard information booklet and letter informing them of their results and the outcome of randomisation. Intervention participants will also be sent a letter informing them of their results and the outcome of randomisation and subsequently contacted to book them onto an education programme.

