### 5.2 Primary Endpoint Analysis

### 5.2.1 Primary Analysis of Primary Endpoints

The primary outcome is change in overall volume of physical activity (average acceleration, ENMO) from baseline to 12 months. For the primary outcome treatment arm will be compared using linear regression modelling with

- 1. a binary indicator for randomisation group as the explanatory variable
- terms for stratification factors (gender and ethnicity) as confounders
- 3. adjustment for the change from baseline in accelerometer wear time and baseline average daily physical activity.

The primary analysis at 12 months will be based on complete data.

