#### 5.2.2.2 Intention-to-treat Population

To allow for full analysis set, missing data will be imputed using a multiple imputation procedure which substitutes predicted values from a regression equation. The imputation will be carried out by the MI command in Stata 15. MI replaces missing values with multiple sets of simulated values to complete the data, performs standard analysis on each completed dataset, and adjusts the obtained parameter estimates for missing-data uncertainty using Rubin's rules to combine estimates 16.

The following procedure will be followed:

- The MI will be set as wide
- The MI will register imputation of the average daily physical activity at 12 months and at baseline

Date:

20/03/2019

Clinical Trials Unit

A regression method will be used, where the registered variables will be individually
adjusted for the randomisation and stratification factors (sex and ethnicity), with 100
imputations to avoid biased estimates, rseed (2259) and the force options

 MI estimate will provide the final results using the same regression model as the primary analysis and covariate adjustments.

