### 5.3 Secondary Endpoint Analyses

The analyses of the secondary outcomes will be conducted in a similar manner as the main analysis using the appropriate model type, logistic regression for binary outcomes, linear for continuous and ordinal for ordinal outcome.

The assumptions of each analysis will be assessed and alternate parameterisations will be considered where appropriate.

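### Household pairs are allocated together, but the primary regression and the analyses that reuse it treat all participants as independent: a small understatement of standard errors that costs almost nothing to correct

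*SAP*

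**What the plan says.** Section 1.2.2 sets 1:1 randomisation of participants, stratified by gender and ethnicity, and then adds an exception: "If two people are taking part from the same household they will be randomised to the same arm to prevent contamination taking place".

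Section 5.2.1 fixes the primary model: "For the primary outcome treatment arm will be compared using linear regression modelling with" three components. These are "a binary indicator for randomisation group as the explanatory variable", "terms for stratification factors (gender and ethnicity) as confounders", and "adjustment for the change from baseline in accelerometer wear time and baseline average daily physical activity". None of them refers to the household, and no variance method other than the regression default is named.

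The other analyses inherit this specification:

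- Per-protocol analysis (5.2.2.1): follows the steps of the primary analysis.
- Multiple imputation (5.2.2.2): "MI estimate will provide the final results using the same regression model as the primary analysis and covariate adjustments".
- Interaction and stratified analyses (5.2.2.3): use the primary model.
- Secondary outcomes (5.3): "The analyses of the secondary outcomes will be conducted in a similar manner as the main analysis using the appropriate model type".
- Subgroups (5.4): apply the principles of the primary analysis.

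Nowhere does the SAP mention a household random effect, cluster-robust standard errors, or an analysis restricted to one member per household.

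**The concern.** Two people allocated as a unit do not contribute two independent allocations. If their outcomes, after covariate adjustment, are more alike than those of two unrelated participants, an ordinary regression overstates the information in the pair. The standard error of the treatment effect is then too small, its confidence interval too narrow, and the type I error above the 5% set in section 4.1.

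Positive correlation is plausible here. The SAP's reason for the rule is contamination, which presumes that co-residents influence each other. The outcome is daily physical activity, and in the intervention arm both members are invited to the same kind of group sessions (1.2.3). The design allows for this dependence and the analysis does not.

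**Working it through.** **1. Does the sample size allow for pairs?** Inputs from section 1.2.6: difference 2.1 mg, SD 5.3 mg, power 80%, significance level 5% (two-sided by section 4.1). A two-sample t calculation on independent observations gives power 0.796 with 100 per arm and 0.8002 with 101 per arm, so 2 × 101 = 202, the SAP's figure. Recruitment: 202/(1 − 0.30) = 288.6, so 289, or 290 in equal arms, again as stated. The target therefore reproduces with no allowance for household pairs.

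**2. Variance factor.** Take an arm with n analysed participants, of whom a share f have their household partner also analysed (f assumed equal in both arms). There are fn/2 pairs, and each adds a covariance term of 2 × ICC × σ². Hence

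Var(arm mean) = (σ²/n²) × (n + fn × ICC) = (σ²/n) × (1 + f × ICC).

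Write D = 1 + f × ICC. Then:

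- true SE = model SE × sqrt(D)
- understatement of the model SE = 1 − 1/sqrt(D)
- true two-sided alpha = 2 × [1 − Φ(1.96/sqrt(D))]
- analysed N needed for the planned power = 202 × D, rounded up

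**3. Results.** The SAP gives no value for f or for the ICC, so every row is an assumption. The ICC is the within-household correlation of the outcome after adjustment.

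| f | ICC | D | Model SE too small by | True alpha | N needed |
|---|---|---|---|---|---|
| 0 | any | 1.000 | 0 | 0.0500 | 202 |
| 1% | 0.1 | 1.001 | 0.05% | 0.0501 | 203 |
| 2% | 0.3 | 1.006 | 0.3% | 0.0507 | 204 |
| 5% | 0.3 | 1.015 | 0.7% | 0.0517 | 206 |
| 10% | 0.3 | 1.030 | 1.5% | 0.0535 | 209 |
| 10% | 0.5 | 1.050 | 2.4% | 0.0558 | 213 |
| 20% | 0.5 | 1.100 | 4.7% | 0.0617 | 223 |

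Worked case, f = 10% and ICC = 0.5: D = 1 + 0.10 × 0.5 = 1.05; sqrt(D) = 1.0247; 1 − 1/1.0247 = 2.4%; 1.96/1.0247 = 1.913, so alpha = 0.0558.

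At 202 analysed, f = 1% is about 1 pair (0.01 × 202/2), f = 10% about 10 pairs, and f = 20% about 20 pairs. In the last row the true SE is 4.9% larger than the model SE (sqrt(1.10) = 1.0488), which is the same as the model SE being 4.7% too small.

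**4. Attrition.** A pair matters only if both members are analysed. If the planned 30% losses were independent within pairs (an assumption, since couples may drop out together), 20% of recruits in pairs would become f = 0.20 × 0.70 = 14%. With ICC = 0.5, D = 1.07 and alpha is about 0.058.

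**The case against.** The strongest counter-argument is size.

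- **Pairs are probably few.** Both members must be 12-36 months past a confirmed cardiac event, reach the walk-test threshold, have access to a mobile phone and consent (1.2.4). This makes the 20% row an extreme rather than an expectation.
- **The residual ICC may be low.** The outcome is change in activity adjusted for baseline activity, so stable habits shared by a household are largely absorbed. Only the remaining correlation counts.
- **Attrition breaks up pairs,** as step 4 shows.

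All three stand, and they are why the main range is f of 1-10% with ICC down to 0.1. They limit the size of the effect but do not remove the mismatch.

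It can also be said that section 5.3 promises to check model assumptions and consider alternatives. That statement sits under secondary endpoints, does not mention clustering, and does not reach the primary model.

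A reader might infer more than the SAP supports:

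- **That this is a cluster-randomised trial analysed at the wrong level.** It is not. Section 1.2.2 randomises participants individually, and the household rule is an exception for co-participating members.
- **That the sample size is undermined.** With f up to 10% and ICC up to 0.5, the analysed number needed rises from 202 to at most 213.
- **That the second member simply inherits the first member's allocation.** The SAP says only that both go to the same arm, and they may be allocated jointly. A sensitivity run on the first-randomised member could therefore be undefined.
- **That every model errs in the same direction.** In gender-stratified models a mixed-sex pair is split between strata, so the understatement need not arise there.

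**Conclusion.** The point holds as a minor mismatch between design and analysis. For participants who share a household, the allocation unit is the household, and no specified model reflects this. The direction, a standard error that is too small for the main treatment effect, rests on two conditions: that some pairs are analysed with both members, and that their residual outcomes are positively correlated. Over the range judged reasonable here the true type I error stays between about 0.050 and 0.056, and even the extreme case gives 0.062. The omission is certain from the text. The magnitude is not, because f and the ICC are both assumed.

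It is still worth correcting before database lock. The number of pairs is not stated, and a variance method chosen after the data have been seen would be open to question.

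**What to change.** In section 5.2.1, state that the primary model uses standard errors clustered by household, with each participant who has no co-participating household member given their own identifier, and that the analyses reusing the model (5.2.2 to 5.4) do the same. Report the number of household pairs by arm. Optionally, add one sensitivity run of the primary model that keeps one randomly chosen member of each pair; random choice works whether pairs were allocated jointly or in sequence.

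The cost is one model option and a sentence or two. The planned Stata software offers clustered variance for linear, logistic and ordinal regression. The allocation rule cannot be applied without knowing who shares a household, so the link should be recoverable, but the SAP does not say that it is held as a data field and this should be confirmed. Nearly all clusters would contain one person, so there are ample clusters for the robust variance, and results will barely change if pairs are rare. The sample size need not be altered.

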### 1.2.3 Study treatment interventions

This will be a randomised control trial with an intervention group and a control group.

1) Intervention group: Participants randomised to the intervention group will receive the standard information leaflet and will be invited to attend two group-based structured education sessions. These education sessions will be delivered by trained facilitators approximately two weeks apart. The participants will receive 82 physical activity related text messages at different weekly frequencies following the second education session up until the 12 month follow-up assessment.

These structured education sessions have been developed and refined in conjunction with PPI work and through the use of existing infrastructure consisting of Diabetes. Education and Self-Management in on-going and Newly Diagnosed (DESMOND) groups and a network of trained facilitators.

2) Control group: Participants randomised to control group will not receive the intervention. Participants will be provided with general health advice in the form of a standard information leaflet and will continue with their 'usual' GP care.

Date:

20/03/2019

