#### 1.2.6 Sample size calculations

The primary outcome is change from baseline to 12 months average daily physical activity, as quantified by the Euclidean norm minus one (ENMO) method measured in milligravity units (mg). This is the main measure of activity derived from the activity monitor that will be used in this study (PACES). In order to detect a minimum clinically significant difference of 2.1 mg, which is equivalent to an overall increase in physical activity volume of approximately 30 minutes of light walking at 4km/h, assuming a standard deviation of 5.3 mg [1], a power of 80% and significance level of 5%, the sample size requires 202 participants. To allow for 20% loss to follow-up and 10% noncompliance of the activity monitor, we will therefore need to recruit 290 participants (145 in each group).

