# 4 General Issues for Statistical Analysis

# 4.1 Multiplicity, Multiple Comparisons and Interim Analyses

All tests and reported p-values will be two-sided, where a p-value of < 0.05 will be considered to be statistically significant. Estimates will be presented with 95% confidence intervals. There will be no formal adjustment for multiple significance testing. The outcomes however, are clearly categorised by the degree of importance (primary and secondary). No formal interim analyses were planned.

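### Only the intervention arm is taught in groups, but the primary model and the sample size treat all participants as independent, so the planned confidence interval is too narrow if outcomes correlate within education groups

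*SAP*

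**What the plan says.** Randomisation is of individuals (SAP 1.2.2: "Participants will be randomised 1:1"), except that two people from one household go to the same arm. After allocation, only intervention participants are brought together: they "will be invited to attend two group-based structured education sessions" (1.2.3), led by trained facilitators and followed by text messages. Controls stay with their usual GP care and a leaflet.

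The sample size (1.2.6) targets a "minimum clinically significant difference of 2.1 mg" with a standard deviation of 5.3 mg and "a power of 80% and significance level of 5%, the sample size requires 202 participants". The increase to 290 is for loss to follow-up and monitor non-compliance only.

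The primary analysis (5.2.1) is a linear regression with "a binary indicator for randomisation group as the explanatory variable", plus gender, ethnicity, change in wear time and baseline activity. The per-protocol and imputation analyses (5.2.2) reuse this model, and the secondary and subgroup analyses (5.3, 5.4) follow its principles. No section mentions a random effect, a cluster-robust variance or a sensitivity analysis for education group or household.

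**The concern.** This is a partially nested design: one arm is grouped after randomisation and the other is not. People taught together share a session and influence one another, so their 12-month activity may be more alike than that of two people from different groups. The mean of the intervention arm then varies more than independent observations imply. A regression with independent errors does not see this extra variation. It reports a standard error that is too small, in the direction that favours declaring an effect.

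The gap lies in the analysis, not only in the planning figures. By naming linear regression and listing its terms, the SAP fixes the error structure, and no secondary or sensitivity analysis would reveal whether it was adequate.

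**Working it through.** **Inputs from the SAP.** Difference 2.1 mg, SD 5.3 mg, power 80%, significance level 5% (1.2.6); two-sided, since "All tests and reported p-values will be two-sided" (4.1); equal allocation (1.2.2); 202 evaluable, so n = 101 per arm.

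**Reproducing the stated size.** The normal formula gives 2 × [5.3 × (1.960 + 0.842)/2.1]² ≈ 100 per arm, or 200 in total. The t-test version gives 101 per arm, or 202 in total, with power 80.02%. Recruitment: 202/0.70 = 288.6, against 290 stated. So 202 is obtained with a design effect of 1 and contains no hidden allowance for groups.

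**Inputs not in the SAP, assumed here.** Evaluable participants per group, m = 6 or 10; ICC = 0.01, 0.02 or 0.05. The total SD is held at 5.3 mg and all 101 intervention participants are counted as grouped.

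**Formulas.**
- Variance of the difference with grouping in one arm: SD²/n + SD² × [1 + (m − 1) × ICC]/n.
- Ratio to the variance assumed by the plan: F = {1 + [1 + (m − 1) × ICC]}/2.
- Shortfall of the planned standard error: 1 − 1/√F.
- Type I error of the planned test: 2 × [1 − Φ(1.960/√F)].
- Power of a correctly adjusted test: Φ(2.816/√F − 1.960), where 2.816 = 2.1/[5.3 × √(2/101)]. With F = 1 this gives 80.4% (normal approximation).

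**Results.**

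| m | ICC | F | √F | SE too small by | Type I error of planned test | Power, adjusted test |
|---|---|---|---|---|---|---|
| 6 | 0.01 | 1.025 | 1.012 | 1.2% | 5.3% | 79.4% |
| 6 | 0.02 | 1.050 | 1.025 | 2.4% | 5.6% | 78.5% |
| 6 | 0.05 | 1.125 | 1.061 | 5.7% | 6.5% | 75.6% |
| 10 | 0.01 | 1.045 | 1.022 | 2.2% | 5.5% | 78.7% |
| 10 | 0.02 | 1.090 | 1.044 | 4.2% | 6.1% | 76.9% |
| 10 | 0.05 | 1.225 | 1.107 | 9.6% | 7.7% | 72.0% |

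In the last row the correct standard error is 10.7% larger than the planned one, which makes the planned one 9.6% too small. A simulation with 100 per arm gave a type I error of 5.6% (m = 10, ICC 0.01) and 7.6% (m = 10, ICC 0.05), in line with the formula.

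**Effect of the planned baseline adjustment on power.** The calculation in 1.2.6 takes no credit for it. If adjustment leaves a fraction k of the variance (k is assumed), power at m = 10 and ICC 0.05 is Φ{2.1/[5.3 × √(k × 2.45/101)] − 1.960}. With k = 0.75 this is about 84%; with k = 0.85, about 79%. The ratio F, and with it the shortfall of the standard error, does not depend on k if the same ICC applies to the adjusted outcome.

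**The case against.** Four points can fairly be made for the plan as it stands.

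**Power.** A reader might infer that the trial has less than 80% power, or has it only if the ICC is zero. The SAP does not support that. The baseline adjustment in 5.2.1 is not counted in 1.2.6 and could restore the loss, as the k = 0.75 case shows. The 72% to 79% range describes the 1.2.6 inputs alone. This objection stands for power, but not for the width of the interval.

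**Type I error.** A reader might also infer that the error rate exceeds 5% outright. If the education changes nobody's activity and groups form without regard to outcome, there is no within-group correlation and no inflation. Inflation needs groups that truly differ around a zero mean effect, or bookings related to outcome. This stands, and the type I figures carry that condition.

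**Group size.** Ten evaluable participants per group is on the high side, since 1.2.6 allows for 30% without usable data. Ten booked would leave about seven: at ICC 0.05, F = 1.15 and type I error is about 6.8%. Non-attendance, which the per-protocol definition in 3.4 anticipates, and the text messages may weaken the correlation by 12 months. These are reasons to expect a small ICC and to estimate it, not to set it at zero without saying so.

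**Facilitators.** The SAP says that facilitators are trained, not how they are assigned, so clustering by facilitator would be inference. The point rests on group delivery alone.

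**Conclusion.** The point holds in a conditional form. The SAP specifies group delivery in one arm only, analyses all participants as independent and sizes the trial the same way. If outcomes correlate within education groups, the planned interval is too narrow, by about 1% to 10% for 6 to 10 evaluable participants per group and an ICC of 0.01 to 0.05. Both ranges are assumptions. At an ICC of 0.01 the effect is small; it becomes material at about 0.05. The documents establish neither that the trial is underpowered nor that its error rate exceeds 5%. They show that the plan assumes zero correlation without stating it and has no means of checking it. The change should be made before database lock, as SAP section 1 allows.

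**What to change.** - **Define the cluster.** Record the education group into which each intervention participant was first booked, and use it as the cluster whether or not the person attended. Treat controls, and anyone never booked, as clusters of one. Keep same-household pairs (1.2.2) in one cluster.
- **Analysis (5.2.1).** Add a random group effect in the intervention arm only, with small-sample degrees of freedom. If that model does not converge, or estimates zero group variance, use cluster-robust standard errors on the same clusters. At minimum, make this a pre-specified sensitivity analysis under 5.2.2. If it becomes the primary model, carry the same allowance into the analyses that reuse it.
- **Reporting.** Report the estimated ICC.
- **Sample size (1.2.6).** State that the 80% power assumes no clustering by education group and takes no credit for baseline adjustment. Do not add participants.

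The cost is some SAP wording, linkage of booking records to the analysis file, and a slightly wider interval if the correlation is above zero. If it is near zero, the result hardly changes and the trial can show that.
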